### 4.2. Study Measures & Methods

**SCREENING**- Participants will answer questions if interested in study participation. If eligible, participants will be transferred to a research trained coach.

**INFORMED CONSENT** – If interested and eligible, participant will hear the consent form read to them by the research trained Quit Coach. The participant may ask questions before giving their consent. The coach will note the participant has provided their verbal informed consent.

**BASELINE SURVEY** – Participant will spend approximately 10 minutes answering baseline assessment questions. Participants will be sent a gift card of their choice for \$15 after completing the baseline survey.

---

## PROTOCOL

---

Table 2. Measures	Screen	Baseline	Program utilization	2-month follow-up
Demographics (gender, age, race/ethnicity, pregnancy/breastfeeding status)	x			
Tobacco/E-Cigarette/Cannabis use		x		x
Self-efficacy & motivation for quitting tobacco		x		x
Cessation medication use				x
Nicotine dependence (cigarettes per day, time to first cigarette)	x			x
Outcomes				
Program satisfaction and acceptability (usefulness, would recommend the program to others)				x
7- and 30-day point prevalence tobacco abstinence. CO-verified tobacco abstinence				x
Treatment Engagement			x	

*Study inclusion/exclusion criteria*

Callers to the MD state quitline 18+, daily smokers, not pregnant/post-partum, enrolling into an English quitline program, are not offered or in another study managed by the Optum quitlines, and have not been previously offered this study will be offered study screening.

If callers agree to be screened for the study: inclusion criteria include possession of a smartphone with a data plan (needed for use of the Vincere app), agreement to download the app onto their phone, agreement to use a personal CO monitoring device.

*Days 1-55*

**Tobacco Cessation Coaching Calls 1-5** – Participants will engage in coaching calls about quitting smoking. There will be brief discussion of the CO monitoring program and smartphone app for Arms 2 and 3. Call 1 may take place on Day 1. Other calls will be scheduled as per standard quitline procedures. Participants will be referred to Vincere's technology helpline for questions about the app and CO device.

**CO monitoring program (Arms 2 and 3)**. Participants will be sent a Vincere "breath pen" CO monitoring device and given instructions to download the Vincere Health smartphone app. The app also has an incentive/gift card feature where money earned is tallied and participants will receive a gift card through text message. This is how incentives will be delivered. Arm 2 and 3 participants will be asked to take 2 CO tests per day; only Arm 3 participants will earn incentives for CO monitoring. Participants will receive regular reminders and reinforcement for CO monitoring via the app.

*Day 55*

Arm 1 receives CO monitoring device and instructions to download Vincere Health smartphone app. They will be asked to try out the Breath Monitor device to make sure they know how to use it and to call Vincere if they experience any issues. On day 60 they will be prompted to complete a CO breath test in the same way as Arms 2 and 3.

*Day 60*

**Follow-up Survey**: Participants will be sent information for completing the follow up survey via the Vincere app. \$20 will be added to the gift card total on the app after survey is completed.

**Biochemical Verification**: If participant self-reports being quit from tobacco at follow up, they will be asked to complete a final CO monitoring test (or tests) to verify quit status. Those who complete this final test will be given an additional \$20 via the app.

PROTOCOL

#### 4.3. Drugs & Devices Being Studied

Participants will be provided access to the Vincere Health smartphone app available for Apple or Android devices. The app will be used for CO monitoring and compliance reminders and delivering survey questions (at end of study). Additionally, participants are sent in the mail an iCOquit "Breath Pen" personal Bluetooth CO monitor with a user guide. The device is classified as a low risk 'general wellness device'. As such, we make no claims that the device will help participants quit; it's only used as a (helpful) tool to monitor progress. There are no restrictions on use.

Nicotine replacement (NRT) is provided by participating state quitlines as part of standard services. NRT is not under investigation in this study.

#### 4.4. Intervention or Observation Procedures

All participants will receive the standard quitline coaching intervention. Coaches will review and discuss CO monitoring compliance and readings with participant in Arms 2 and 3. Arm 2 and 3 participants will be asked to take 2 CO tests per day; only Arm 3 participants will earn incentives for CO monitoring. Participants will receive regular reminders and reinforcement for CO monitoring via the app. Voice recording is standard procedure for all quitline calls. Calls are reviewed to ensure coaches are following study protocols.

#### 4.5. Data Sources and Variables

Research Question/Aim/Objective:	Data Variables:	Data Source

 
To determine eligibility
 
	
 
Enrollment screening
 
	
 
Service utilization (Apollo – Clinical Management System)
 

 
To determine tobacco quit outcomes
 
	
 
Baseline and follow-up survey
 
CO readings
 
	
 
Datstat (Survey software)
 
VH app & CO monitor
 

 
To determine satisfaction with the program
 
	
 
Follow up survey
 
Data from VH App
 
	
 
Service utilization (Apollo – Clinical Management System)
 
VH app & CO monitor
 

 
Treatment Engagement
 
	
 
Call completion
 
	
 
Service utilization (Apollo – Clinical Management System)
 

See screening and survey documents for full outline of data variables.

#### 4.6. Justification of Sample Size & Power

For the study there will be 300-up to 350 individuals per participating Optum state quit line (currently only Maryland is participating). The target recruitment was selected based on estimates regarding how many

## PROTOCOL

participants could be recruited in the given time frame. This pilot study is not powered to detect a significant difference, but outcomes will be used to determine the need for continued study.

#### 4.7. Statistical Methods

For the proposed pilot study we plan to use summary statistics with confidence intervals (CIs), means with standard errors (SE) and graphical displays (histograms, pie charts, Box plots, etc.) as appropriate to describe participant self-reported demographic characteristics, use of tobacco and other variables measured at baseline and at 2 months. We will use logistic or linear regression analyses to compare intervention and control groups on: mean number of calls completed; proportion completing at least two calls and, at 2 months, mean satisfaction ratings, mean change in cigarettes per day (cpd) and smoking cessation rates. We will conduct sensitivity analyses to determine the potential range of treatment effects on abstinence taking into account 1) different assumptions concerning the probability of relapse among survey non-responders, 2) substitution of biochemical results for those who claimed abstinence in the absence of agreement, and 3) the application of biochemical validation confirmation rate of abstinence to individuals who claimed abstinence but did not return their biochemical test results. Our analyses will include independent variables for state and gender to increase precision. We stratified randomization by state because of state variability and by gender because of the impact that gender has on treatment engagement and tobacco cessation. We will address missing values in three ways; 1) we will analyze responders only, 2) we will impute missing tobacco use as 'smoking' and 3) we will conduct sensitivity analyses (as discussed above) by modeling the proportion of smokers among non-respondents, and the applying of biochemical validation results to individuals who stated that they were abstinent.

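### For people who claim abstinence but have no CO test, Section 4.7 names one verified-status rule, which removes unequal test completion from that analysis and leaves lower values not clearly covered

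*Combined protocol and SAP*

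**What the plan says.** Section 4.7 (Statistical Methods) states the aim: "We will conduct sensitivity analyses to determine the potential range of treatment effects on abstinence". It lists three elements.

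1. For people who do not answer the survey, the input is varied: "different assumptions concerning the probability of relapse among survey non-responders".
2. For people whose claim and test disagree, the test decides: "substitution of biochemical results for those who claimed abstinence in the absence of agreement".
3. For people who claim abstinence and have no test, one rule is given: "the application of biochemical validation confirmation rate of abstinence to individuals who claimed abstinence but did not return their biochemical test results".

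The same section handles missing values in three ways: responders only, then "we will impute missing tobacco use as 'smoking" (the second way), then a reference back to the sensitivity analyses. It does not say whether the confirmation rate is pooled or estimated by arm, how its uncertainty is carried, or that test completion will be reported by arm.

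Table 2 in Section 4.2 lists the abstinence outcomes as "7- and 30-day point prevalence tobacco abstinence. CO-verified tobacco abstinence", and none is named as primary. Payment for the final test is the same in all arms (Sections 4.2 and 5.6): "Those who complete this final test will be given an additional" $20.

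**The concern.** A claimant without a test is a different kind of missing case from a survey non-responder. The claim is known and only its verification is absent. Section 4.7 varies the assumption for non-responders but gives one value for untested claimants. That value assumes they are as truthful as those who tested.

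The design gives reasons to expect test completion to differ by arm. Arms 2 and 3 are asked to test twice a day for about 55 days, and Arm 3 is paid per test. Arm 1 is sent the device only at the end (Day 55 in Section 4.2, 60 days after randomization in Section 4.1), and Section 5.6 allows about 5 days for mailing. Section 5.5 adds a mailed print survey for people who do not answer in the app, so a claim can arrive with no test.

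At stake is how the pilot is read. Section 4.6 says its outcomes will inform whether to study further, and Section 4.13 ties product development to signs of better quit rates. A range that holds this input at one value may look narrower than the data allow.

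**Working it through.** The documents state no claim rate, test-completion rate or confirmation rate, so there is no figure of the plan's own to reproduce. Every rate below is an assumption.

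**Formula.** Let s = share claiming abstinence, t = share of claimants tested, c = testers' confirmation rate, and k = confirmation rate assumed for untested claimants. Then

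verified rate = s × [t × c + (1 − t) × k].

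**The plan's rule** sets k = c:

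s × [t × c + (1 − t) × c] = s × c.

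Test completion t drops out. The cancellation is exact when c is taken by arm, or is the same in all arms. The plan does not say which applies.

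**Illustration.** s = 25% in both arms; t = 50% in Arm 1 and 80% in Arm 3; c = 80%.

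| k in untested claimants | Arm 1 | Arm 3 | Difference (points) |
|---|---|---|---|
| k = c = 0.8 (plan's rule) | 0.25 × (0.40 + 0.40) = 20.0% | 0.25 × (0.64 + 0.16) = 20.0% | 0 |
| k = 0.4 in both | 0.25 × (0.40 + 0.20) = 15.0% | 0.25 × (0.64 + 0.08) = 18.0% | +3 |
| k = 0 in both | 0.25 × 0.40 = 10.0% | 0.25 × 0.64 = 16.0% | +6 |
| k = 1 in both | 0.25 × (0.40 + 0.50) = 22.5% | 0.25 × (0.64 + 0.20) = 21.0% | −1.5 |
| Arm 1 k = c, Arm 3 k = 0 | 20.0% | 16.0% | −4 |
| Arm 1 k = 0, Arm 3 k = c | 10.0% | 20.0% | +10 |

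**Direction.** With equal s and c and a common k, the difference is s × (t in Arm 3 − t in Arm 1) × (c − k). Its sign follows the completion gap. If the split is reversed (80% in Arm 1, 50% in Arm 3), k = 0 gives 0.25 × (−0.3) × 0.8 = −6 points.

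**With a difference in claims.** Take s = 25% in TAU and 35% in an intervention arm, c = 80%, and about 117 per arm (350/3, assuming equal allocation, which is not stated). Wald 95% intervals are in brackets and treat each verified rate as a simple proportion.

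- Plan's rule: 20.0% v 28.0%, +8.0 (−2.9 to 18.9), whatever the completion.
- k = 0 in both, 70% tested in both arms: 14.0% v 19.6%, +5.6 (−4.0 to 15.2).
- k = 0 in both, 50% TAU v 80% intervention tested: 10.0% v 22.4%, +12.4 (3.1 to 21.7).
- k = 0 in both, 80% TAU v 50% intervention tested: 16.0% v 14.0%, −2.0 (−11.2 to 7.2).

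The shifts from the plan's +8.0 (down 2.4, up 4.4, down 10.0) compare with an interval half-width of about 11 points.

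**Uncertainty in c.** At 117 per arm and s = 25% there are about 29 claimants. If half are tested, c rests on about 15 people. Its standard error is √(0.8 × 0.2 / 15) = 0.10, or about ±20 points at 95%. Treating c as known would hide this.

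**The case against.** The strongest counter-argument is that Section 4.7 is a set of analyses, and the testers' rate is only one of them. Self-reported abstinence is an outcome in its own right and takes untested claimants at their word (k = 1). Element 2, read alone, also leaves their claims standing. With the inputs above it gives 22.5% v 21.0%, so unequal completion does move an analysis that the plan already names. This stands: the cancellation belongs to element 3, not to the plan as a whole, and the testers' rate is not the most favourable value available.

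It can also be said that imputing missing tobacco use as smoking covers an untested claimant when the outcome is CO-verified abstinence, since verified status is then missing. The text allows that reading. It also allows the opposite one, because the claimant's tobacco use was reported and element 3 treats this group separately. What stands is an ambiguity, so the plan cannot be said to exclude the rule.

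A reader might go further and infer that the plan reports only the optimistic end of the treatment effect and overstates quit rates. The documents do not support that. A lower quit rate is not the same as a smaller treatment effect: in the illustration the plan's rule gives 0, while counting the untested as smoking gives +6 in favour of Arm 3. Nor does any figure show that people who skip the paid test are more often smoking. In Arm 1, late delivery of the device is an equally ready explanation.

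Finally, this is a pilot that Section 4.6 describes as not powered to detect differences. That limits the weight of the point but does not remove it, because the stated aim is a range.

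**Conclusion.** The point holds as a gap in the sensitivity analysis. For verified status in untested claimants the plan names one value, k = c. That value makes test completion drop out of the analysis, and values below c are not clearly included. The effect on the treatment difference can go either way, depending on which arm tests less and on whether k differs by arm.

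Under the equal-claims illustration (25% claiming, 50% v 80% tested, c = 80%), the plan's rule gives 0. A common k between 0 and 1 gives +6 to −1.5, and k varied by arm between 0 and c gives −4 to +10. These sizes rest wholly on assumed rates; the cancellation itself does not. The consequence is for interpretation and for the decision on further study. It is a low-cost improvement and does not undermine the design.

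**What to change.** In Section 4.7:

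- Replace the single value for untested claimants with a tipping-point table: k from 0 to 1, including c, varied separately by arm.
- State that counting untested claimants as smoking is one of the scenarios. This settles what the missing-as-smoking rule covers.
- Estimate c by arm, or state that it is pooled, and carry its uncertainty by multiple imputation or bootstrap.
- Report CO-test completion among claimants by arm.

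Setting k = 0 in every arm would not be enough on its own: it can enlarge the difference, as in the +6 and +12.4 results, so the by-arm variation is needed. The cost is a few lines of code and one more table, with no new data. The downside is a wider reported range.

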## 5.7. Diversity Considerations:

TARGETED/PLANNED ENROLLMENT: Number of Subjects			
Ethnic Category	Females	Males	Total
Hispanic or Latino	67	45	1012
Not Hispanic or Latino	178207	112131	290338
Ethnic Category: Total of All Subjects *	184214	116136	300350
Racial Categories			
American Indian/Alaska Native	2	1	3
Asian	1214	89	2023
Native Hawaiian or Other Pacific Islander	1	1	2
Arab or Arab American	1	42	23
Black or African American	8599	5262	137159
White	8498	5260	136158
Racial Categories: Total of All Subjects *	185215	115135	300350

These estimates are representative of the target population: existing callers into a single state quitline (Maryland).

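### The model for change in cigarettes per day does not name baseline cigarettes per day as a covariate, although the value is already collected

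*Combined protocol and SAP*

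**What the plan says.** Section 4.7 sets out the comparison of arms: "We will use logistic or linear regression analyses to compare intervention and control groups on" a list of outcomes that includes, at 2 months, "mean satisfaction ratings, mean change in cigarettes per day (cpd) and smoking cessation rates". For a continuous change score this means linear regression. The same section then names the covariates and gives the reason for them: "Our analyses will include independent variables for state and gender to increase precision". No other covariate is named there or elsewhere in the document.

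The baseline value exists. Table 2 in Section 4.2 has the row "Nicotine dependence (cigarettes per day, time to first cigarette" and marks it at screening and at the 2-month follow-up. Section 4.1 places screening before consent and randomisation.

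On the state covariate, Section 4.6 notes "currently only Maryland is participating", and Section 5.7 describes the target population as "existing callers into a single state quitline (Maryland". On purpose, Section 4.6 says: "This pilot study is not powered to detect a significant difference".

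**The concern.** The plan adopts covariate adjustment to gain precision but leaves out the variable that should give the most for this outcome. With one state enrolled, the state column is constant. It is harmless, but it explains no variance. That leaves gender.

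Forming a change score is not the same as adjusting for baseline. Subtraction fixes the slope on the baseline value at 1, whereas regression estimates it. Fixing the slope at the wrong value costs precision. It also leaves part of any chance baseline difference between arms in the estimated effect.

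What is at stake is the width of one confidence interval. The pilot reports estimates with intervals and uses them to judge whether further study is needed. The sample size was set by how many people could be recruited, so extra precision for this outcome has to come from the analysis.

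**Working it through.** The plan gives no SD, correlation, effect size or power for this outcome, so there is no figure to reproduce. The check compares the two analyses over a range of assumptions.

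**Inputs from the document:** three arms (Section 4.1); 300 to 350 participants (Section 4.6).

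**Assumptions:** equal allocation, giving 300/3 = 100 or 350/3 ≈ 117 per arm; the same SDs and correlation in every arm, taken within gender because gender is in both models. Baseline SD is s, 2-month SD is k·s, and the correlation between them is rho. I use rho = 0.3, 0.5, 0.7 and k = 0.75, 1, 1.25.

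**Variance per participant, in units of s²**

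- Change score without baseline: 1 + k² − 2·rho·k
- Change score adjusted for baseline: k²(1 − rho²)
- Difference: (1 − k·rho)²

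The difference is a square, so in large samples under these assumptions adjustment never increases the variance. It reaches zero only when k·rho = 1. The formulas use only variances and the correlation. They do not require normal data, which matters because quitters will report zero cigarettes.

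**Variance ratio, adjusted over unadjusted**

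| k | rho 0.3 | rho 0.5 | rho 0.7 |
|---|---|---|---|
| 0.75 | 0.5119/1.1125 = 0.46 | 0.4219/0.8125 = 0.52 | 0.2869/0.5125 = 0.56 |
| 1 | 0.91/1.40 = 0.65 | 0.75/1.00 = 0.75 | 0.51/0.60 = 0.85 |
| 1.25 | 1.4219/1.8125 = 0.78 | 1.1719/1.3125 = 0.89 | 0.7969/0.8125 = 0.98 |

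At k = 1 the ratio simplifies to (1 + rho)/2. There the standard error falls by 19%, 13% and 8%, which is equivalent to 1/0.65 = 1.54, 1/0.75 = 1.33 and 1/0.85 = 1.18 times the sample for this outcome.

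**95% CI half-width for two arms, in baseline SDs, k = 1**

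The formula is 1.96 × sqrt(2/n) × sqrt(variance). At n = 100, 1.96 × sqrt(2/100) = 0.277. At n = 60 (60% response, assumed), it is 0.358.

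| n per arm | rho 0.3 | rho 0.5 | rho 0.7 |
|---|---|---|---|
| 100 | 0.328 to 0.264 | 0.277 to 0.240 | 0.215 to 0.198 |
| 60 | 0.42 to 0.34 | 0.36 to 0.31 | 0.28 to 0.26 |

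For scale, if the baseline SD were 10 cigarettes per day (assumed), the rho = 0.5 interval at 100 per arm would narrow from about ±2.8 to ±2.4 cigarettes per day.

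**Chance baseline imbalance**

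The standard error of the baseline difference between two arms is sqrt(2/n): 0.141 SD at 100 per arm, 0.131 at 117, and 0.183 or 0.169 at 60 or 70 (60% response). For a given baseline difference, the unadjusted change score carries a fraction 1 − k·rho of it into the estimate, with sign reversed.

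| k | rho 0.3 | rho 0.5 | rho 0.7 |
|---|---|---|---|
| 0.75 | 0.78 | 0.63 | 0.48 |
| 1 | 0.70 | 0.50 | 0.30 |
| 1.25 | 0.63 | 0.38 | 0.13 |

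Adjustment removes this component.

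**The case against.** The strongest reply is that nothing here is wrong. An unadjusted change score estimates the right quantity without bias under randomisation. Section 4.7 says the analyses will include state and gender, not that they will include nothing else. The outcome is also peripheral: the hypotheses in Section 1 concern app download and CO compliance, calls completed, and cessation and satisfaction. Section 4.13.1 bases product decisions on compliance, satisfaction, quit rates and engagement. No stated decision turns on the width of this interval. Finally, the size of the gain rests on values the documents do not give, and at k = 1.25 and rho = 0.7 it is only 2% of the variance.

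Most of this stands, and it sets the weight of the point. It does not remove it. A covariate that is not named is not pre-specified, and choosing between adjusted and unadjusted results after seeing the data is an avoidable freedom. The size of the gain is uncertain, but its direction is not, because the variance difference is a square. The state term needs no criticism: it is written for possible further states and costs nothing while it is constant.

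**Conclusion.** The point holds as a minor improvement in efficiency, not a defect in validity. Section 4.7 adjusts for precision but omits the baseline value of the outcome. With equal SDs and rho between 0.3 and 0.7, including it cuts the variance of the arm contrast by 15% to 35%. Over k from 0.75 to 1.25 the cut runs from about 2% to 54%. These sizes rest on assumed correlations and SD ratios and on common variances across arms. The half-widths also assume equal allocation and the stated response. That adjustment helps, or at worst does no harm in large samples, does not depend on the assumed rho and k.

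**What to change.** Add one sentence to Section 4.7: the linear model for change in cigarettes per day includes cigarettes per day at screening as a covariate, together with gender as the stratification factor, and state if a second state enrols. Change can stay as the outcome, because once baseline is in the model the arm contrast and its standard error are the same as when the 2-month value is analysed.

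The cost is one sentence and one degree of freedom. No new data, participants or procedures are needed.
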